- 15. Performance status must be recorded as ECOG and will be performed at screening, Day 1 of every cycle, at EOT, and as needed according to investigator's discretion based on new symptoms and/or medical concerns. Refer to the Appendix 1 for conversion between ECOG and KPS.
- 16. HRQoL will be performed at screening. Day 1 of every other treatment cycle starting from Cycle 3 to 24, at EOT, and at every disease assessment (see Footnote 28 for timing of disease assessments).
- 17. Recorded from 21 days prior to the first administration of BNT321 to EOT or safety FU visits. Includes prescription medications, over-the-counter medications, and supplements.
- Adverse events will be collected and reported from the signing of the trial-specific ICF until safety FU.
- 19. ECGs will be performed at screening and on Day 1 of every cycle for C1 through C3. On these days ECGs are obtained prior to treatment, at t_{max}, and at end of last mFOLFIRINOX infusion. Investigators may obtain ECGs at additional timepoints in Cycle 4 to 12 if indicated based on results in Cycle 1 to 3. ECGs will also be obtained

Clinical Trial Protocol BNT321-02

Page 18 of 127 Version: 2.0 Date: 22 JAN 2024

- prior to first BNT321 administration on Cycle 13, and at EOT and as clinically indicated during BNT321 monotherapy per assessment of the trial investigator. ECGs are performed as triplicate exams at all study timepoints per Section 8.3.3.
- 20. Complete blood count (CBC) with differential to include WBC, RBC, HGB, HCT, platelets, MCV, and MCH to be performed at screening, Day 1 of every cycle, EOT, at safety FU visit, and as needed according to investigator's discretion based on new symptoms and/or medical concerns.
- 21. Blood chemistry to include sodium, potassium, chloride, bicarbonate, blood urea nitrogen, creatinine, glucose, calcium, phosphate, magnesium, AST, ALT, total bilirubin, alkaline phosphatase, total protein, albumin, and uric acid to be performed at screening, Day 1 of every cycle, EOT, at safety FU visit, and as needed according to investigator's discretion based on new symptoms and/or medical concerns.
- 22. Serum amylase, -lipase and haptoglobin will be performed on Day 1 of every cycle and EOT, and as needed according to investigator's discretion based on new symptoms and/or medical concerns.
- 23. GGT will be performed at screening and on Day 1 of every cycle and as needed according to investigator's discretion based on new symptoms and/or medical concerns.

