- 24. To include color, appearance, glucose, bilirubin, ketone, specific gravity, blood, pH, protein, urobilinogen, nitrite, leukocyte esterase. If warranted by dipstick analysis, microscopic analysis to include RBC, WBC, casts, crystals, epithelial cells, and bacteria. Will be performed at screening, and when clinically indicated.
- 25. For POCBPs only.
- 26. CA19-9 will be measured from blood collected at screening (post-operative measurement required within 3 weeks of C1D1), C1D1, during PK sampling, on days of BNT321 administration and at disease assessment time points detailed in Footnote 25. During BNT321 monotherapy every 3 months (12 weeks), every 2 years (±7 days), and then every 6 months for 3 years. For all collections on BNT321 administration days, blood will be collected both pre-infusion and post-infusion (end of infusion [EoI] +5 min [± 5 min]). For further details, refer to Table 3.
- 27. For a full pharmacokinetic profile and in-depth sampling, blood will be collected on C2D3 and C3D3, (pre-infusion, EoI +5 min] ± 5 min], EoI +1 h [±15 min] and EoI +4 h [±30 min]). For Cycles 4 onwards, only C_{trough} (pre-infusion) and C_{max} (EoI +5 min [±5 min]) will be drawn on day of BNT321 administration. All other timepoints will include only one blood draw timepoint per day. For further details, refer to Table 3.
- 28. Disease assessment will consist of imaging by CT/MRI scan and serum CA19-9 and will be performed at screening (baseline post-operative imaging within 4 weeks of C1D1 and serum CA19-9 within 3 weeks of C1D1 are required), and then after C1D1 every 3 months (12 weeks) for 2 years and then every 6 months for 3 years (±7 days). CT with contrast or MRI (as appropriate for patient, or multiparametric MRI following an inconclusive CT). Patients should be evaluated with the same imaging method (CT or MRI) throughout the trial.
- 29. Anti-drug antibodies will be measured from blood collected prior to dosing of mFOLFIRINOX on C1D1, C3D1, C6D1, and at EOT.
- 30. ADCC, CDC and cytokines will be measured from blood collected prior to dosing of mFOLFIRINOX and/or BNT321 on days of trial drug administration. Collected on the following days: C1D1, C2D3, C2D8, C4D3, C4D8, C16D1 and C16D5. For Cycle 4 collections, should be adjusted to C4D1 and C4D5 if BNT321 administration is given on C4D1. Whole blood collected for PBMC isolation for ADCC assessment will only be collected if logistically manageable.

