- 31. FFPE tumor tissue from surgical resection is required during screening. In the event of progression, if a biopsy is performed, a sample (optional) should be requested.
- 32. For ctDNA assessment, blood will be collected at C1D1, C6D1, C18D1, and at time of progression. Additional information on sample submission is included in the laboratory manuals.
- 33. Randomization should be done between Day -3 and C1D1.

ical Trial Protocol Page 19 of 127

BNT321-02 Version: 2.0

Date: 22 JAN 2024

- 34. BNT321 in randomized Phase II part of this trial will be administered following the completion of the 5-FU infusion (i.e., on Day 3 of each cycle from Cycle 2 onwards and on Day 1 during the monotherapy part of the protocol, as per Footnote 3). Day 1 administration of BNT321 may be utilized throughout the Phase II part of the trial, following review of Phase I safety data and alignment with the SRC.
- 35. mFOLFIRINOX will be administered as per Section 6.1.

Abbreviations: ADCC = antibody-dependent cell-mediated cytotoxicity; ALT = alanine aminotransferase; AST = aspartate aminotransferase; CnDn = cycle number day number; CA19-9 = sialyl-Lewis A (sLe^a) antigen; CDC = complement-dependent cytotoxicity; CT = computed tomography; ctDNA = circulating tumor DNA; d = days; DFS = disease-free survival; DPD = dihydropyrimidine dehydrogenase; ECG = electrocardiogram; ECOG = Eastern Cooperative Oncology Group; Eol = end of infusion; EOT = end of treatment; 5FU = 5-flourouracil; FFPE = formalin-fixed paraffin-embedded tissue; FU = follow-up; GGT = gamma-glutamyl transferase; h = hours; HGB = hemoglobin; HCT = hematocrit; HRQoL = health-related quality of life; IHC = immunohistochemistry; KPS = Karnofsky performance status; min = minutes; MCH = mean corpuscular hemoglobin; MCV = mean corpuscular volume; MRI = magnetic resonance imaging; PDAC = pancreatic adenocarcinoma; PK = pharmacokinetics; POCBP = patient of childbearing potential; RBC = red blood cell; SCR = screening; SRC = safety review committee; TB = tuberculosis; t_{max} = time required to reach C_{max}; UGT1A1 = UDP glucuronosyltransferase family 1 member A1; WBC = white blood cell.

Page 20 of 127 Version: 2.0 Date: 22 JAN 2024

Table 3: Supplementary table for PK – Phase I and Randomized Phase II - combination arm (mFOLFIRINOX + BNT321)

		Cycle 1			Cycle 2-	-3			Су	rcle 4–24	
Assessment for Phase I	SCR	D 4	Day of BNT321 administration						Day of BNT321 administration		

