- 20. Blood chemistry to include sodium, potassium, chloride, bicarbonate, blood urea nitrogen, creatinine, glucose, calcium, phosphate, magnesium, AST, ALT, total bilirubin, alkaline phosphatase, total protein, albumin, and uric acid to be performed at screening, Day 1 of every cycle, Week 25/EOT, at safety FU visit, and as needed according to investigator's discretion based on new symptoms and/or medical concerns.
- 21. Serum amylase, lipase and haptoglobin will be performed on Day 1 of every cycle, Week 25/EOT, and as needed according to investigator's discretion based on new symptoms and/or medical concerns.

Page 24 of 127 Version: 2.0 Date: 22 JAN 2024

- 22. GGT will be performed at screening and on Day 1 of every cycle, Week 25/EOT, and as needed according to investigator's discretion based on new symptoms and/or medical concerns.
- 23. To include color, appearance, glucose, bilirubin, ketone, specific gravity, blood, pH, protein, urobilinogen, nitrite, leukocyte esterase. If warranted by dipstick analysis, microscopic analysis to include RBC, WBC, casts, crystals, epithelial cells, and bacteria. Will be performed at screening, and when clinically indicated.
- 24. For POCBPs only.
- 25. CA19-9 will be measured from blood collected at screening (post-operative measurement required within 3 weeks of C1D1), C1D1, at EOT and at disease assessment timepoints detailed in Footnote 23.
- 26. Disease assessment will consist of imaging by CT/MRI scan and serum CA19-9 and will be performed at screening (baseline post-operative imaging within 4 weeks of C1D1 and serum CA19-9 within 3 weeks of C1D1 are required), and then after C1D1 every 3 months (12 weeks) for 2 years, and then every 6 months for 3 years (±7 days). CT with contrast or MRI (as appropriate for patient, or multiparametric MRI following an inconclusive CT). Patients should be evaluated with the same imaging method (CT or MRI) throughout the trial.
- 27. ADCC, CDC and cytokines will be measured from blood collected prior to dosing of mFOLFIRINOX. Collected on the following days: C1D1, C2D3, C2D8, C4D3, and C4D8. Whole blood collected for PBMC isolation for ADCC assessment will only be collected if logistically manageable.
- 28. FFPE tumor tissue from surgical resection is required during screening. In the event of progression, if a biopsy is performed, a sample (optional) should be requested.

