To explore the relationship of clinical outcome with baseline* status of tumor resection classification R0 or R1, and resection nodal status pN0 or pN1.	Tumor resection classified for each patient as R0 (no tumor <1 mm from margin) or R1 (tumor within 1 mm from margin), RCP**. Tumor nodal status classified for each patient as pN0 (no nodal disease) or pN1 (nodal involvement in resection).
To determine mFOLFIRINOX dose intensity when administered with and without BNT321.	 The mFOLFIRINOX relative dose intensity (RDI), defined for each patient as the fraction of (cumulative chemotherapy dose received/ treatment duration) planned dose intensity. Number of patients receiving RDI ≥70%.

^{*} Baseline is defined as last value prior to initiation of trial treatment.

Page 43 of 127 Version: 2.0 Date: 22 JAN 2024

** RCP classification. Tumors designated R0 CRM+ (R0 narrow) according to CRM concept will be stratified as R1 tumor in this trial.

Abbreviations: AE = adverse event; ADA = anti-drug antibody; ADCC = antibody-dependent cell-mediated cytotoxicity; AUC = area under the curve; CDC = complement-dependent cytotoxicity; C_{max} = maximum serum concentration that the drug achieved after administration; ctDNA = circulating tumor deoxyribonucleic acid; CTCAE = US National Cancer Institute Common Terminology Criteria for Adverse Events; CRM = circumferential resection margin; DLT = dose-limiting toxicity; EOT = end of treatment; ECG = electrocardiogram; EORTC = European organisation for research and treatment of cancer; HRQoL = health-related quality of life; ICF = informed consent form; IMP = investigational medicinal product; mDFS = median disease-free survival; NA = not applicable; OS = overall survival; PDAC = pancreatic ductal adenocarcinoma; PD = pharmacodynamic; PK = pharmacokinetics; RCP = Royal College of Pathologists; RFS = relapse-free survival; RDI = relative dose intensity; RP2D = recommended Phase II dose; SAE = serious adverse event; TEAE = treatment-emergent adverse event; t_{max} = time required to reach C_{max}.

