6.6.2 Randomization

For Phase II, part 2, patients will be randomized in a 1:1 fashion to one of two treatment arms, mFOLFIRINOX + BNT321 or mFOLFIRINOX alone. Randomization will be conducted in the trial's interactive web response system (IWRS) up to 3 days before Cycle 1 Day 1. Randomization will include stratifications to ensure balanced enrollment between the two arms for the following characteristics: tumor resection status (R0 vs R1) and tumor nodal status at resection (pN0 vs pN1).

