9.4 Analysis sets

The following analyses sets are defined:

Analysis set	Description
Screened Set	All patients who gave informed consent
Enrolled Set	All patients who are enrolled into the trial
Full Analysis Set (FAS)	All patients who are randomized into the trial
Modified Full Analysis Set (mFAS)	All patients who received IMP and have a baseline and at least one on- treatment / post-treatment tumor response assessment and satisfy major eligibility criteria
Safety Analysis Set (SAF)	All patients who received IMP (i.e., at least one dose of IMP)
DLT Evaluation Set	All patients who are enrolled in the dose escalation part of the trial (Phase I) and who meet at least one of the following criteria: • Experiences a DLT following at least one dose of BNT321

Page 87 of 127 Version: 2.0 Date: 22 JAN 2024

Analysis set	Description
	Does not experience a DLT, has received at least 80% of the planned BNT321 dose, and is followed for the full DLT assessment period
Per Protocol Set (PP)	All patients who are randomized into the trial and absent of important protocol deviations (as identified throughout the conduct of the trial and before each data cut-off) which are considered to impact the analyses
PD Set	All patients with baseline and at least one valid on-treatment follow-up PD assessment
PK Set	All patients with baseline and at least one valid on-treatment follow-up PK assessment

Abbreviations: DLT = dose-limiting toxicity; IMP = investigational medicinal product; PD = pharmacodynamic; PK = pharmacokinetic.

All safety analyses will be based on the treatment actually taken by the patient ('as treated'). All other analyses will be based on the treatment the patient was assigned / randomized to ('as randomized'), unless stated otherwise.

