9.5.1 General considerations

In general, the statistical analyses will be performed for Phase I and Phase II parts separately. The Phase I part analysis will be performed by dose level cohort. The Phase II part will be performed by treatment group (i.e., mFOLFIRINOX + BNT321 and mFOLFIRINOX).

Continuous variables will be summarized by treatment group/cohort using the following descriptive statistics: number of patients (n), mean, standard deviation, median, minimum and maximum

Categorical variables will be summarized by treatment group/cohort presenting absolute and relative frequencies (n and %) of patients in each category.

Time-to-event-endpoints will be analyzed using Kaplan-Meier methodology by treatment group/cohort and censored in accordance with the FDA Guidance: "Clinical Trial Endpoints for the Approval of Cancer Drugs and Biologics" and the EMA guidance "Guideline on the

Page 88 of 127 Version: 2.0 Date: 22 JAN 2024

evaluation of anticancer medicinal products in man". Censoring rules will be defined in the SAP.

The median survival time (including two-sided 95% confidence limits according to Brookmeyer and Crowley) and the first and third quartile will be presented for each treatment group/cohort. Survival rates and DFS rates (including two-sided 95% confidence interval based on the Greenwood 1926 formula) as well as the number and percentage of patients with events, censored and under risk will be displayed for selected time points (e.g., at 12, 24, 36 and 48 months).

The survival distributions for two treatment groups will be compared using the stratified log-rank test (stratified by the stratification factors surgical resection status and nodal status at time of resection), and the p-value will be provided. The associated HR and two-sided 95% confidence interval will be estimated by using stratified (i.e., R0 versus R1; pN0 versus pN1) Cox proportional hazard model with treatment as model covariate.

The time-to-event analysis will be illustrated using Kaplan-Meier plots by treatment group and additionally strata. Baseline is defined as last available value prior to randomization (Phase II)/first dose of IMP (Phase I).

Data up to and including the clinical cut-off date for the statistical analysis will be included in the statistical analysis. Handling of missing data will be described in the SAP.

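### The Phase II baseline rule rejects the pre-dose C1D1 sample for patients already randomized, so for measures with no screening draw PD Set membership depends on whether the site draws blood or randomizes first

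*Combined protocol and SAP*

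**What the plan says.** Section 9.5.1 gives one baseline rule, with no exception by parameter: "Baseline is defined as last available value prior to randomization (Phase II)/first dose of IMP (Phase I".

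On randomization, Table 2 footnote 33 and Table 4 footnote 30 both say "Randomization should be done between Day -3 and C1D1". Section 6.6.2 puts it "up to 3 days before Cycle 1 Day 1".

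On sampling:
- ADCC, CDC and cytokines, combination arm (Table 2 footnote 30): "Collected on the following days: C1D1, C2D3, C2D8, C4D3, C4D8, C16D1 and C16D5".
- The same assays, control arm (Table 4 footnote 27): "Collected on the following days: C1D1, C2D3, C2D8, C4D3, and C4D8".
- Laboratory analytes, combination arm (Table 2 footnote 22): "Serum amylase, -lipase and haptoglobin will be performed on Day 1 of every cycle and EOT". Table 4 footnote 21 is equivalent for the control arm.
- ctDNA in both arms, and ADA in the combination arm, also start at C1D1.

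None of these has an entry in the screening column of Table 2 or Table 4. Section 9.4 defines the PD Set as "All patients with baseline and at least one valid on-treatment follow-up PD assessment", and Section 9.5.3 bases the PD analysis on that set.

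**The concern.** The rule is anchored to an event that can come before the only pre-treatment sample. A patient randomized on Day -2 and bled on C1D1 before chemotherapy has a sound pre-treatment sample for every measure listed, yet the rule does not admit it because it was taken after randomization.

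Two planned analyses suffer. ADCC/CDC activity is a secondary endpoint analysed on the PD Set, so membership would depend on the order in which a site does two things within a few days of each other. That order is a logistical matter and has nothing to do with whether the patient is evaluable. Section 9.5.4 also plans change-from-baseline summaries and shift tables for laboratory parameters, and amylase, lipase and haptoglobin would have no baseline for the same patients.

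**Working it through.** The plan attaches no figure to this point. Its one design figure, 164 DFS events, does not depend on baseline. The check sets the schedule against the rule.

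**Step 1. First scheduled sample in Phase II (Tables 2 and 4 with footnotes)**

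| Measure | Screening sample | First scheduled draw | Arms |
|---|---|---|---|
| ADCC/CDC/cytokines | No | C1D1 | Both |
| ctDNA | No | C1D1 | Both |
| ADA | No | C1D1 | Combination only (Section 8.8) |
| Amylase | No | C1D1 | Both |
| Lipase | No | C1D1 | Both |
| Haptoglobin | No | C1D1 | Both |
| GGT, hematology, chemistry, CA19-9, HRQoL (for contrast) | Yes | Screening | Both |

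The gap is therefore specific to six measures in the combination arm and five in the control arm.

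**Step 2. Order of blood draw and randomization**

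Section 1.3 requires assessments to precede treatment. Nothing requires them to precede randomization. Footnote 1 of Tables 2 and 4 gives procedures not scheduled on Day 3 a window of ±3 days. C1D1 blood may therefore be drawn over the same span in which randomization is allowed. Four cases follow:

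| Randomized | C1D1 blood drawn | Accepted as baseline by 9.5.1? |
|---|---|---|
| Day -3 to Day -1 | On C1D1, before dosing | No |
| Day -3 to Day -1 | Earlier in the window, before randomization | Yes |
| C1D1 | Same day, before randomization | Yes |
| C1D1 | Same day, after randomization but before dosing | No |

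All four samples precede any drug. Only the order relative to randomization separates them.

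**Step 3. Count at nominal visit days**

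For randomization on Day -3, -2 or -1 with blood on C1D1, the qualifying scheduled values are 0 of 6 (combination) and 0 of 5 (control). If baseline were the last value before the first dose of trial treatment, the same samples would give 6 of 6 and 5 of 5.

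**Step 4. What depends on baseline**

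- PD Set: membership requires a baseline, so the "No" rows are excluded.
- Amylase, lipase and haptoglobin: Section 9.5.4 first names hematology, blood chemistry and urinalysis, then refers to the parameter list in Section 8.3.4, which includes these three outside its chemistry line. Change and shift tables for them are the natural reading, though not an explicit one.
- ctDNA: exploratory, with no baseline-dependent analysis specified.
- CA19-9: has a screening value. The rule would take that value, up to 3 weeks before C1D1, over a post-randomization C1D1 value, but no change-from-baseline analysis is stated for it.
- DFS, OS and RFS: no baseline value enters them.

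**The case against.** The strongest reply is that the ±3-day window lets sites draw C1D1 blood before randomizing, so a baseline is possible for everyone. That stands as far as it goes. The window permits the right order but does not secure it, and the protocol gives sites no reason to prefer it.

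A second reply is that PD results are summarized by visit, not as change from baseline. That is correct, so the harm to the PD endpoint comes only through exclusion from the PD Set.

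A third is that the SAP can settle this. Section 9 does let the SAP modify the outline, with an amendment needed only for major changes to primary endpoint definitions or analyses. This makes the repair easy. But 9.5.1 states the baseline rule outright, so a SAP that simply carried it forward would carry the problem too.

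Three stronger readings are tempting and are not supported:

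- *A reader might infer that everyone randomized before C1D1 lacks a baseline, so that up to 300 patients are affected or the PD Set is empty.* The order of draw and randomization decides, not the randomization day. Those figures describe only a worst case in which no site bleeds first.
- *A reader might infer that pre-existing ADA cannot be separated from ADA formed on treatment.* Section 9.5.3 analyses immunogenicity on the FAS with patient listings. The C1D1 ADA sample precedes mFOLFIRINOX, and BNT321 starts only at C2D3. Whatever it is called, that sample remains a pre-BNT321 value.
- *A reader might infer that Section 3 contradicts 9.5.1, since its footnote says "Baseline is defined as last value prior to initiation of trial treatment".* The asterisk attaches to resection and nodal status, which are settled at surgery. The footnote is not a general rule for laboratory or PD values. The two wordings are worth aligning, but they are not a direct contradiction.

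**Conclusion.** The point holds and is wrong as written: a stated rule discards valid pre-treatment samples, which is more than missing detail. Its reach is the Phase II PD Set and any baseline-referenced summary of amylase, lipase and haptoglobin. The primary analysis and the survival endpoints are untouched, and no ADA data are lost.

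The number of patients affected cannot be determined from the documents. It runs logically from none, if every site bleeds before randomizing, to every Phase II patient, if none does. Nothing in the protocol places the trial within that range.

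The conclusion assumes that 9.5.1 is applied literally and that it is the general rule for Phase II, as its placement and unqualified wording suggest. It should be corrected before database lock.

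**What to change.** In Section 9.5.1 and the SAP, for measures that are not time-to-event:

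- In both phases, define baseline as the last non-missing value before the first dose of any trial treatment, meaning mFOLFIRINOX on C1D1. Do not leave this as first dose of IMP: if that were read as BNT321 alone, which starts at C2D3, baseline could fall after chemotherapy had begun.
- For patients randomized but never treated, who remain in the FAS, use the last value on or before randomization.
- Keep randomization as time zero for Phase II time-to-event endpoints, and keep the strata as recorded at randomization.

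The cost is a short text change, with no new samples or visits. The small downside is that a baseline may be taken up to about 3 days after open-label randomization, though always before any drug. HRQoL, where knowing the arm could matter most, is not scheduled at C1D1, so its scheduled baseline remains the screening questionnaire.
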